5.3.2. Estimand

Primary Trial Objective: To evaluate the efficacy of guselkumab compared to placebo, in combination with a 26-week glucocorticoid (GC) taper regimen, in adult participants with new-onset or relapsing giant cell arteritis (GCA).

Clinical Question of Interest: For a patient with new-onset or relapsing GCA, what would the expected effect of being assigned guselkumab together with the protocol allowed background 26-week GC-taper medication on the likelihood of experiencing a treatment response at Week 28?

5.3.2.1. Primary Estimand

The primary estimand, based on the above primary objective, is defined by the following 5 components which assess the treatment effects not only based on the variable measurements, but also based on intercurrent events:

- **Study intervention:**
 - Guselkumab in addition to 26-week GC-taper (including participants who received 400 mg IV induction doses followed by 200 mg SC dosing from Week 12 onwards and participants that received 200 mg SC dosing only)
 - Placebo in addition to 26-week GC-taper
- **Population:** adult participants 50 years or older with active new-onset or relapsing GCA (defined by American College of Rheumatology criteria).
- **Variable:** Binary response variable, where a responder is defined as a participant achieving GC-free remission at Week 28. A participant with an intercurrent event in categories 1-3 defined below will be considered as a non-responder.
- **Summary Measure (Population-level summary):** difference in the proportions of GC-free remission at Week 28 between the guselkumab group and the placebo group.
- **Intercurrent Events:**

Intercurrent Events (ICEs)	Strategy for Addressing Intercurrent Events and Its Description
1. Discontinuation (DC) of study intervention due to lack of efficacy or an AE of worsening of GCA. 2. Initiation of a protocol-prohibited medication during the study that could improve GCA. 3. Initiation of GC rescue therapy.	Composite Strategy: A participant with this intercurrent event is considered as a non-responder after this event. The occurrence of this intercurrent event is captured in the variable definition.
4. Discontinuation of study intervention other than ICEs #1	Treatment Policy: Use observed data regardless of whether or not this intercurrent event had occurred

Note: For participants experiencing multiple ICEs, an ICE in categories 2 or 3 will override an ICE in category 4.

5.3.2.2. Supplementary Estimand

5.3.2.2.1. Supplementary Estimand 1 (Hypothetical Strategy Estimand)

In this supplementary estimand, the only component that changes from the definition of the primary estimand is that the hypothetical strategy will be used for addressing ICEs 1-4.

Hypothetical strategy: assess the treatment effect as if the intercurrent event would not have occurred. Under the hypothetical strategy, data collected after ICEs 1-4 will not be used in analysis and will be imputed using a MAR multiple imputation method.

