Participants who develop a GCA flare or are unable to adhere to the protocol-defined 26-week open-label GC tapering regimen because of ongoing disease activity should stop the protocol-defined GC taper and be given open-label rescue therapy with GCs at the discretion of the investigator. When considering use of rescue GC, a careful assessment should be made by the investigator whether the symptoms are related to a GCA flare (failure of taper) or are more likely due to non-inflammatory symptoms which could represent adrenal insufficiency or other comorbidities.

The participant may continue to receive blinded study agent administrations and continue in the study if it is in the best interest for the participant in the opinion of the investigator. Treatment with GC and/or other GCA medication will be at the discretion of the investigator for the further duration of the study. If other GCA medication is required, the medical monitor or designee should be contacted and treatment with study intervention should be discontinued. A wash-out period of 12 weeks is recommended before starting treatment with biologic therapies.

The date and time of rescue medication administration as well as the name and dosage regimen of the rescue medication must be recorded.

Participants who require rescue therapy for their GCA disease during the protocol-defined GC taper and up to Week 28 will be deemed non-responders in the primary endpoint analysis.

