3. SAMPLE SIZE DETERMINATION

Approximately 51 participants are planned to be randomized into the study. The assumptions for the sample size and power calculation were based on the data from the Actemra Phase 3 GCA study. In the Actemra Phase 3 study, the proportions of participants in GC-free remission at Week 28 were estimated to be approximately 38% and 74% for placebo (+26-week GC taper) and Actemra qw (+26-week GC-taper), respectively, for a treatment difference of 36%.

Based on the data above, the GC-free remission rates at Week 28 are assumed to be 40% for placebo and 80% for guselkumab treatment arm. Based on these assumptions, 51 participants are planned to be randomized in a 2:1 ratio to either the guselkumab group (N=34) or the placebo

group (N=17). These sample sizes provide the study with 82% power to detect a difference in the primary endpoint between the 2 study intervention groups.

Table 1 shows the power to detect a difference in proportions of participants in GC-free remission between the guselkumab and placebo intervention groups at Week 28 under various assumptions.

Table 1: Power to Detect Difference in Proportions of Participants Achieving Glucocorticoid-free Remission between the Guselkumab and Placebo Intervention Groups at Week 28

Placebo (n = 17)	Guselkumab (n = 34)	Power (%)
35%	70%	68
	75%	81
	80%	90
40%	75%	69
	80%	82
	85%	91

Notes:

- The power calculation is based on two-sample Z test with continuity correction (pooled variance) under the normal distribution approximation.
- Power calculation is based on a 2-sided significance level of 0.10.
- Total sample size is 60.

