5.3.1. Definition of Endpoint

GC-free remission response at Week 28 is defined as:

1. No signs or symptoms of active GCA at Week 28
AND
2. Absence of GCA flare from first dose of the study agent through Week 28,
AND
3. Adherence to the protocol specified 26-week GC taper

Definition of GCA Flare: GCA flare is defined as the recurrence of signs and symptoms of active GCA, with or without elevation of inflammatory markers, and with the necessity for an increase in GC dose for GCA.

Having CRP/ESR elevations in isolation without clinical signs and symptoms attributable to GCA, does not qualify as flare, unless the investigator decided to increase the GC dose.

Definition of GC Taper Adherence. The protocol specified 26-Week open-label GC tapering schedule is provided in Section 10.8 of the protocol. Adherence to this schedule is required. Participants will remain on the GC dose they were on at baseline for one week (Week 0). The taper is starting at Week 1 and continues down to GC-free in Week 26, as per the schedule. Participant should adhere to the tapering schedule through Week 26 unless they require use of rescue GC therapy for GCA disease flare.

A participant will be considered as not adherent to the protocol-defined 26-week GC taper, if the compliance of GC intake (any oral GC intake) is greater than 120% cumulative prednisone (or equivalent) dose, between first and last planned dose of GC taper. Patients not adhering to the GC

taper will be considered as non-responders in the primary analysis. Participants receiving less than the planned amount of prednisone (or equivalent) will not be considered as non-responders.

Compliance of GC intake will be calculated as follows:

Compliance (%) = (actual GC dose taken/total GC dose supposed to be taken) x100.

If a participant receives GC other than prednisone or prednisolone, the amount of GC dosage equivalent to prednisone recorded on Concomitant Therapy page in the eCRFs will be converted to a prednisone-equivalent dose using the following table.

GC	Conversion factor from alternative GC to prednisone equivalent dose (mg)
Cortisone acetate	0.2
Hydrocortisone	0.25
Deflazacort	0.67
Prednisone	1
Prednisolone	1
Triamcinolone	1.25
Methylprednisolone	1.25
Dexamethasone	6.67
Betamethasone	6.67

The following rules will be used to assess a GC-free remission at Week 28:

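### Supplementary Estimand 1 imputes Week 28 response for participants who have already failed on GCA, which can shrink a true treatment difference

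*SAP*

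**What the plan says.** SAP 5.3.1 makes GC-free remission at Week 28 depend on three conditions: no active signs or symptoms at Week 28, no flare at any time from first dose to Week 28, and adherence to the taper. A flare is a recurrence of signs and symptoms "with the necessity for an increase in GC dose for GCA". Protocol 6.8.3 says that participants who need rescue for GCA during the taper and "up to Week 28 will be deemed non-responders in the primary endpoint analysis".

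SAP 5.3.2.1 lists four intercurrent events (ICEs):

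- ICE 1: discontinuation for lack of efficacy or an adverse event of worsening GCA
- ICE 2: a prohibited medication that could improve GCA
- ICE 3: GC rescue
- ICE 4: discontinuation for any other reason

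ICEs 1-3 get the composite strategy, and the Variable component itself counts them as non-response. ICE 4 gets treatment policy.

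For Supplementary Estimand 1, SAP 5.3.2.2.1 states that "the only component that changes from the definition of the primary estimand is that the hypothetical strategy will be used for addressing ICEs 1-4", and that "data collected after ICEs 1-4 will not be used in analysis and will be imputed using a MAR multiple imputation method". SAP 5.3.4.1 carries this out. Data after an ICE become missing, and Week 28 response is imputed by fully conditional logistic regression on arm, the two stratification factors and remission status from Week 4 onward. For that remission status it points to SAP 5.5.1.3, which defines normalization of CRP and ESR instead.

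**The concern.** A hypothetical strategy suits an event that hides the outcome of interest. ICE 1 and GCA-driven ICE 3 do not hide the outcome; they are ways of failing it. Had rescue been withheld from a participant who flared, the flare would still have happened and Week 28 would still be a non-response. Imputation under missing at random (MAR) does not answer that question. It gives the participant the outcome that same-arm participants without an ICE tended to have, and most of those are responders.

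The text also pulls two ways. If only the ICE strategy changes, the endpoint still requires absence of flare through Week 28, and the Variable sentence still counts ICEs 1-3 as non-response, so there is little to impute. If SAP 5.3.4.1 is followed literally, failures that are already determined are overwritten. Two programmers could follow the SAP and report different results.

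At stake is how a prespecified supplementary result would be read. Placebo is expected to have more failures, so its rate is raised more. A real effect could then appear not to survive this analysis for a reason unrelated to missing data.

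**Working it through.** **1. The plan's own figure.** The inputs are in SAP 3. On the rates, it says that "the GC-free remission rates at Week 28 are assumed to be 40% for placebo and 80% for guselkumab treatment arm". The allocation is 34 to guselkumab and 17 to placebo, 51 in all. The test is a two-sample Z test with pooled variance and a continuity correction, at a two-sided alpha of 0.10.

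- Pooled rate = (17×0.4 + 34×0.8)/51 = 0.667
- Null SE = √(0.667×0.333×(1/17+1/34)) = 0.140
- Alternative SE = √(0.24/17 + 0.16/34) = 0.137
- Continuity correction = 0.5×(1/17+1/34) = 0.044
- Power = Φ((0.40 − 0.044 − 1.645×0.140)/0.137) = 0.820

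This matches the stated 82%, so 40% against 80% is the right baseline.

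**2. Effect of imputing failures.** Let p be an arm's rate under the primary estimand and f the share of its non-responders with an ICE 1-3. The documents do not give f, so a range is shown. If earlier visits carry no information, MAR imputation within arm gives an expected rate of

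p / (p + (1 − p)(1 − f)).

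Example at f = 0.75: placebo 0.4/(0.4 + 0.6×0.25) = 0.727; guselkumab 0.8/(0.8 + 0.2×0.25) = 0.941.

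| f (both arms) | Placebo | Guselkumab | Difference (points) | Share of 40 points lost |
|---|---|---|---|---|
| 0.25 | 47.1% | 84.2% | 37.2 | 7% |
| 0.50 | 57.1% | 88.9% | 31.7 | 21% |
| 0.75 | 72.7% | 94.1% | 21.4 | 46% |
| 0.90 | 87.0% | 97.6% | 10.6 | 74% |

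Half the difference is lost only when f exceeds about 0.77.

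**3. Unequal shares.** With f = 0.9 on placebo and 0.5 on guselkumab, the rates are 87.0% and 88.9%, a difference of 1.9 points. With the shares reversed they are 57.1% and 97.6%, a difference of 40.4 points, so nothing is lost.

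**4. Informative earlier visits.** A large-sample sequential logistic imputation was run with 60,000 participants, visits from Week 4 to Week 28, and arm and earlier statuses as predictors (strata omitted). Responders were active at an earlier visit with probability 0.05. Non-responders were active with probability 0.05, 0.30 or 0.60 (uninformative, moderate, strong). These probabilities are assumptions. Remaining difference in points:

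| f | Flare visit | Uninformative | Moderate | Strong |
|---|---|---|---|---|
| 0.50 | set missing | 31.7 | 35.3 | 37.3 |
| 0.50 | kept | 31.6 | 39.5 | 39.5 |
| 0.75 | set missing | 21.4 | 29.5 | 35.7 |
| 0.75 | kept | 20.5 | 37.8 | 38.8 |
| 0.90 | set missing | 11.1 | 23.0 | 32.3 |
| 0.90 | kept | 10.2 | 34.1 | 37.9 |

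So the loss depends on how well earlier visits predict outcome and on whether the flare visit stays in the data. The SAP settles neither, because its cross-reference for earlier remission status leads to CRP/ESR normalization and it gives no rule for the flare visit.

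**5. Where f might lie.** SAP 5.3.1 gives three routes to non-response: flare, stable active disease at Week 28, and GC intake above 120% of plan. A flare entails a GC increase, so most flares will also be ICE 3. The observed failures left to inform the model are mainly the other two routes. A high f is therefore plausible, but it is not documented. At f = 0.9, the expected number of observed placebo failures is 17×0.6×0.1 ≈ 1.

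**The case against.** The strongest reply is textual. Only data after the event are discarded, and the endpoint definition is unchanged. A flare recorded at or before rescue is pre-event data, so Week 28 is already a known non-response and the difference would hardly move. That reading is coherent and the SAP does not exclude it. However, SAP 5.3.4.1 imputes after an ICE without exception, and on the reply's reading the hypothetical strategy would have almost nothing to do for flare-driven rescue. The ambiguity is a reason to settle the text.

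A reader might infer that most of the arm difference is removed. The documents do not support that. It needs a share above about 0.77 in both arms, or a higher share on placebo, together with weakly predictive earlier visits. A reader might also infer that failures are imputed only from participants who did not fail. That is too strong: the participants informing the model include observed non-responders, and earlier status is meant to be a predictor.

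Two further points stand. Not all rescue is GCA failure, since Protocol 6.8.1 lets participants with adrenal insufficiency use rescue GC; for them a hypothetical question is legitimate. And this analysis is supplementary. The primary estimand is composite, treatment-policy and per-protocol analyses sit beside it, and no decision rule depends on it.

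**Conclusion.** The concern holds as a matter of estimand definition. Supplementary Estimand 1 treats events that are mostly failures as if they concealed the outcome, and its imputation step conflicts with the flare condition in SAP 5.3.1 and the Variable in SAP 5.3.2.1. If the imputation is done as written in SAP 5.3.4.1 and the ICE share is similar in both arms, the bias is towards no difference.

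The planned 40 points fall to about 37, 32, 21 or 11 when 25%, 50%, 75% or 90% of failures have an ICE 1-3. That rests on the planning rates, an equal share in both arms and uninformative earlier visits. Informative visits reduce the loss, and unequal shares move it from none to nearly all. No power is given for this analysis, because the imputation model is not fully defined.

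A reader might infer that the primary result is at risk. It is not: SAP 5.3.3 counts ICEs 1-3 as non-response there.

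**What to change.** In SAP 5.3.2.2.1 and 5.3.4.1:

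- Keep ICE 1, ICE 3 for GCA, and ICE 2 given for GCA as non-response.
- State that a flare recorded by Week 28 fixes Week 28 status as non-response.
- Limit the hypothetical strategy with MAR imputation to ICE 4 and to ICE 2 or ICE 3 events not due to GCA, such as GC given for adrenal insufficiency. Classify by indication, because SAP Appendix 8 also lists oral GC for other indications as prohibited, so the same event could be coded as either ICE.
- Amend the statement that only the ICE strategy changes so that it agrees with the Variable.
- Correct the reference to SAP 5.5.1.3 so that earlier remission status is defined.

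This is SAP wording only and needs no new data beyond the recorded reason for GC use. The cost is that fewer participants are imputed and the result lies closer to the primary analysis. If the sponsor wants the broader hypothetical question, the SAP should justify it and say how a flare before the event is handled.

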5.3.2.2.2. Supplementary Estimand 2 (Treatment Policy Estimand)

Treatment policy estimand has the same components as the primary estimand, except for the strategies used for the intercurrent events 1-4:

Treatment policy strategy: assess the treatment effect regardless of whether or not intercurrent events had occurred. Under the treatment policy strategy, the observed data after the intercurrent event will be used in analysis.

5.3.3. Analysis Methods for the Primary Estimand

The primary endpoint will be compared between the guselkumab group and the placebo group at Week 28 based on the primary estimand (Section 5.3.2.1) and the data from all participants in FAS (Section 4) will include data from all randomized participants who received at least one administration of study intervention based on their assigned intervention group, regardless of the actual intervention received.

The primary endpoint will be analyzed using the primary estimand. Participants with ICEs 1-3 before Week 28 will be considered as GC-free remission non-responders at Week 28. Participants with ICE 4, observed data after this ICE will be utilized in the analysis. For participants experiencing multiple ICEs, an ICEs 2 or 3 will override an ICE in category 4.

After accounting for the ICEs for the primary estimand, the remaining missing data of the primary endpoint at Week 28 will be considered as a non-responder.

In this primary analysis, the proportion of participants who achieve GC-free remission at Week 28 will be summarized for each intervention group. To address the primary objective, Cochran-Mantel-Haenszel chi-square statistic stratified by baseline disease status (new-onset and relapsing GCA), and the baseline GC dose (≤ 30 mg/day or > 30 mg/day) at a 2-sided significance level of 0.10 will be used. Difference in response rates between the guselkumab group and the placebo group at Week 28 adjusted for baseline disease status (new-onset and relapsing GCA), and the baseline GC dose (≤ 30 mg/day or > 30 mg/day) using Mantel-Haenszel weight and the corresponding 90% CI will be presented. Baseline disease status (new-onset and relapsing GCA), and the baseline GC dose (≤ 30 mg/day or > 30 mg/day) entered into IWRS are to be used. Similar analyses using the observed baseline disease status (new-onset and relapsing GCA), and the observed baseline GC dose (≤ 30 mg/day or > 30 mg/day) will be performed as sensitivity analyses.

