6.3. Measures to Minimize Bias: Randomization and Blinding

Intervention Allocation - Procedures for Randomization and Stratification

Central randomization will be implemented in this study. Participants will be randomly assigned to 1 of 2 intervention groups based on a computer-generated randomization schedule prepared before the study by or under the supervision of the sponsor. The randomization will be balanced by using randomly permuted blocks and will be stratified by new-onset and relapsing GCA and baseline GC use (≤ 30 mg/day or > 30 mg/day). The interactive web response system (IWRS) will assign a unique intervention code, which will dictate the intervention assignment and matching study intervention kit for the participant. The requestor must use his or her own user identification and personal identification number when contacting the IWRS and will then give the relevant participant details to uniquely identify the participant.

Blinding

To maintain the study blind, the study intervention container will have a label containing the study name, study intervention number, reference number, and storage conditions. The label will not identify the study intervention in the container. However, if it is necessary for a participant's safety, the study blind may be broken, and the identity of the study intervention ascertained. The study intervention number will be entered in the eCRF when the study intervention is administered. The study interventions will be identical in appearance and will be packaged in identical containers.

The investigator will not be provided with randomization codes. The codes will be maintained within the IWRS, which has the functionality to allow the investigator to break the blind for an individual participant.

Data that may potentially unblind the intervention assignment (ie, study intervention serum concentrations, anti-guselkumab antibodies, study intervention preparation/accountability data, intervention allocation, biomarker, or other specific laboratory data) will be handled with special care to ensure that the integrity of the blind is maintained and the potential for bias is minimized. This can include making special provisions, such as segregating the data in question from view by the investigators, clinical team, or others as appropriate until the time of DBL and unblinding.

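### The 90% CI for the primary treatment difference has no stated interval type; the usual Mantel-Haenszel Wald forms cover about 84-89% with 17 placebo participants in 4 strata

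*SAP*

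**What the plan says.** SAP 5.3.3 addresses the primary objective with a Cochran-Mantel-Haenszel (CMH) test at two-sided 0.10, "stratified by baseline disease status (new-onset and relapsing GCA), and the baseline GC dose" (≤30 or >30 mg/day). That makes 2 × 2 = 4 strata. It then presents the stratum-adjusted difference in response rates "using Mantel-Haenszel weight and the corresponding 90% CI will be presented".

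The same interval is planned in SAP 5.3.4.2 (Supplementary Analysis 2) and in SAP 5.4.1.3.1 for the binary secondary endpoints at Week 28. SAP 5.3.4.1 (Supplementary Analysis 1) also gives a Mantel-Haenszel-weighted difference with a 90% CI, combined over 500 imputations, and SAP 5.3.4.3 (Supplementary Analysis 3) reuses that method. Protocol 9.4.2 asks for the difference and its 90% CI without further detail. No section names the variance or interval type, or says how sparse strata are handled.

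SAP section 3 plans 51 participants at 2:1, that is 34 on guselkumab and 17 on placebo. On the rates, "the GC-free remission rates at Week 28 are assumed to be 40% for placebo and 80% for guselkumab treatment arm".

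**The concern.** Seventeen placebo participants over four strata is about four per stratum. Relapsing disease may fill 70% of the places or more (SAP 1.2), which could thin the new-onset strata further. Large-sample variance formulas for a stratified difference are unreliable at that size. The plug-in variance p(1−p)/n is too small on average by the factor (n−1)/n. A stratum whose few placebo participants all have the same outcome contributes no placebo variance at all.

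The interval is the trial's main statement of effect size. If it covers less than its label says, it misstates the uncertainty of the proof-of-concept result. It can also exclude 0 when the CMH p-value is above 0.10, and the SAP has no rule for reading that combination. Leaving the type open also leaves the choice to be made after the data are seen.

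**Working it through.** **Inputs.** From SAP section 3: n = 34 and 17, rates 80% and 40%, and the cited earlier-trial rates 74% and 38%. From SAP 5.3.3: four strata, Mantel-Haenszel weights, 90% level (z = 1.645), missing data counted as non-response, so every treated participant enters. From Protocol 6.3: "The randomization will be balanced by using randomly permuted blocks". Block size and the GC-dose split are not given. Assumed: blocks of 3 or 6; stratum shares equal, 35/35/15/15 or 49/21/21/9; or fixed placebo counts of 4/4/4/5 or 7/5/3/2.

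**The plan's own figure.** SAP section 3 states: "The power calculation is based on two-sample Z test with continuity correction (pooled variance) under the normal distribution approximation". For 40% vs 80%:
- pooled rate = (17 × 0.40 + 34 × 0.80)/51 = 0.667
- null SE = √[0.667 × 0.333 × (1/17 + 1/34)] = 0.1400
- alternative SE = √(0.24/17 + 0.16/34) = 0.1372
- continuity correction = 0.5 × (1/17 + 1/34) = 0.0441
- power = Φ[(0.40 − 0.0441 − 1.645 × 0.1400)/0.1372] = Φ(0.915) = 82.0%, against 82% stated.

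The six table cells come out at 67.9, 80.5, 90.1, 69.2, 82.0 and 91.3, against 68, 81, 90, 69, 82 and 91. The table therefore belongs to N = 51, although its footnote in the SAP says 60.

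**Why the plug-in interval is short.** With equal strata there are 17/4 = 4.25 placebo and 34/4 = 8.5 guselkumab participants per stratum.
- true variance ≈ 0.24/17 + 0.16/34 = 0.01412 + 0.00471 = 0.01882
- expected plug-in variance ≈ 0.01412 × 3.25/4.25 + 0.00471 × 7.5/8.5 = 0.01080 + 0.00415 = 0.01495
- ratio of SEs = √(0.01495/0.01882) = 0.891
- half-width ≈ 1.645 × √0.01495 = 0.201, against 1.645 × √0.01882 = 0.226 needed
- normal-theory coverage = 2Φ(1.645 × 0.891) − 1 ≈ 85.7%, before the variability of the SE itself takes a little more.

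**Simulation** (100,000-200,000 trials per scenario). With w = n₁n₀/N in each stratum, the difference is d = Σw(p₁ − p₀)/Σw. Two standard errors were used:
- Greenland-Robins (plug-in): Var = Σw²[p₁(1−p₁)/n₁ + p₀(1−p₀)/n₀]/(Σw)²
- Sato: Var = (dΣP + ΣQ)/(Σw)², with P = [n₁²x₀ − n₀²x₁ + n₁n₀(n₀−n₁)/2]/N² and Q = [x₁(n₀−x₀) + x₀(n₁−x₁)]/(2N).

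The twelve rate sets were five of the six power-table pairs, 38/74, three with no difference, 40/60, and two with rates that vary by stratum.

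| Nominal 90% interval | Coverage at 40/80 | Coverage, all scenarios run | Excludes 0 at 40/40 | Mean width at 40/80 |
|---|---|---|---|---|
| Greenland-Robins | 84.2-84.5% | 83.9-85.2% | about 15% | 0.40 |
| Sato | 87.6-88.2% | 87.1-88.9% | about 12% | 0.44 |
| Stratified Miettinen-Nurminen | 90.0-90.3% | 89.8-90.3% | about 10% | 0.43 |

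The Miettinen-Nurminen row rests on four rate pairs under the three random stratum mixes. Mantel-Haenszel-weighted Newcombe intervals covered 89.4-90.3% with random stratum sizes and 88.4-91.1% with fixed ones.

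At 40/40 the CMH test rejects in 10.0% of trials. The interval excludes 0 while CMH p > 0.10 in about 5% of trials with Greenland-Robins and about 2% with Sato. An unstratified Wald interval also covers only about 87-88% at this size.

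**The case against.** The strongest reply is that the SAP names no interval, so nothing in it is shown to be wrong. A Miettinen-Nurminen or Newcombe interval with Mantel-Haenszel weights would satisfy the sentence in 5.3.3 and would cover about 90%. This stands as a limit on the claim. A reader might infer that the trial's planned interval is known to be too narrow, and the documents do not support that. They support only that the natural reading gives an interval off its level and that nothing in the text rules that reading out.

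A second inference would be that both usual versions are too narrow. Only the plug-in version is. Sato is slightly wider on average than the score interval (0.44 against 0.43) and still undercovers. Since an unstratified Wald interval falls short by a similar amount, the Sato shortfall is mainly ordinary small-sample error; sparse strata explain the extra plug-in loss. The 15% against 10% clash is likewise a plug-in figure.

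A third would be that the primary test is anti-conservative, or that every binary secondary result is affected. The CMH test keeps its 10% level, and no planned decision rests on the interval. SAP 5.4.1.3.1 ties this interval to Week 28; for the by-visit summaries it gives only the missing-data rule.

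Finally, the choice between Miettinen-Nurminen and Newcombe is partly preference, since they perform comparably. What matters is that one is named in advance.

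**Conclusion.** The point holds as a gap with a measurable consequence. On the usual reading, the 90% interval for the primary difference falls about 5-6 percentage points short of its level with the plug-in variance and about 1-3 points short with Sato. No scenario reached 90% with either. The effect is on the reported interval and its agreement with the p-value. The primary test, the power and the estimand are untouched. Block size, stratum shares and stratum-level rates are assumptions, but coverage moved by less than 2 points across them for each method. It is worth correcting because this interval is the main effect estimate and the remedy is cheap; it does not threaten the trial's conclusion.

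**What to change.** In SAP 5.3.3, 5.3.4.2 and 5.4.1.3.1 (Week 28), state that the 90% CI is the stratified Miettinen-Nurminen score interval with Mantel-Haenszel weights; Mantel-Haenszel-weighted Newcombe is an acceptable alternative. Keep the CMH test for the p-value.

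For the multiply imputed analyses in SAP 5.3.4.1 and 5.3.4.3, state separately which variance of the weighted difference is computed in each imputed dataset and combined, because a score interval does not pass directly through that combination step.

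The cost is SAP wording and standard code, settled before the Week 28 database lock. Weights, strata, estimand, test and sample size stay as they are. At 40% vs 80% the score interval is about 7% wider than the plug-in version and slightly narrower than Sato.
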